6.4 TOXICITY CRITERIA

The following adverse event management guidelines are intended to ensure the safety of each patient while on the study. The descriptions and grading scales found in the revised NCI Common Terminology Criteria for Adverse Events (CTCAE) version 5.0 will be utilized for AE reporting. All appropriate treatment areas should have access to a copy of the CTCAE version 5.0. A copy of the CTCAE version 5.0 can be downloaded from the CTEP web site (http://ctep.cancer.gov/protocolDevelopment/electronic_applications/ctc.htm).

7 NIH REPORTING REQUIREMENTS / DATA AND SAFETY MONITORING PLAN

7.1 DEFINITIONS

Please refer to definitions provided in Policy 801: Reporting Research Events found at: <https://irbo.nih.gov/confluence/pages/viewpage.action?pageId=36241835#Policies&Guidance-800Series-ComplianceandResearchEventReportingRequirements>.

7.2 OHSRP OFFICE OF COMPLIANCE AND TRAINING / IRB REPORTING

7.2.1 Expedited Reporting

Please refer to the reporting requirements in Policy 801: Reporting Research Events and Policy 802 Non-Compliance Human Subjects Research found at:

<https://irbo.nih.gov/confluence/pages/viewpage.action?pageId=36241835#Policies&Guidance-800Series-ComplianceandResearchEventReportingRequirements>.

Note: Only IND Safety Reports that meet the definition of an unanticipated problem will need to be reported per these policies.

7.2.2 IRB Requirements for PI Reporting at Continuing Review

Please refer to the reporting requirements in Policy 801: Reporting Research Events found at: <https://irbo.nih.gov/confluence/pages/viewpage.action?pageId=36241835#Policies&Guidance-800Series-ComplianceandResearchEventReportingRequirements..>

7.3 NCI CLINICAL DIRECTOR REPORTING

Problems expeditiously reviewed by the OHSRP in the NIH eIRB system will also be reported to the NCI Clinical Director/designee; therefore, a separate submission for these reports are not necessary.

In addition to those reports, all deaths that occur within 30 days after receiving a research intervention should be reported via email unless they are due to progressive disease.

To report these deaths, please send an email describing the circumstances of the death to [contact] within one business day of learning of the death.

7.4 DATA AND SAFETY MONITORING PLAN

7.4.1 Principal Investigator/Research Team

The clinical research team will meet on a weekly basis when patients are being actively treated on the trial to discuss each patient. Decisions about dose level enrollment and dose escalation if applicable will be made based on the toxicity data from prior patients.

All data will be collected in a timely manner and reviewed by the principal investigator or a lead associate investigator. Events meeting requirements for expedited reporting as described in section [7.2.1](#) will be submitted within the appropriate timelines.

The principal investigator will review adverse event and response data on each patient to ensure safety and data accuracy. The principal investigator will personally conduct or supervise the investigation and provide appropriate delegation of responsibilities to other members of the research staff.

8 SPONSOR SAFETY REPORTING

8.1 DEFINITIONS

8.1.1 Adverse Event

Any untoward medical occurrence in a patient or clinical investigation subject administered a pharmaceutical product and which does not necessarily have a causal relationship with this treatment. An adverse event (AE) can therefore be any unfavorable and unintended sign (including an abnormal laboratory finding), symptom, or disease temporally associated with the use of a medicinal (investigational) product, whether or not related to the medicinal (investigational) product (ICH E6 (R2)).

8.1.2 Serious Adverse Event (SAE)

An adverse event or suspected adverse reaction is considered serious if in the view of the investigator or the sponsor, it results in any of the following:

- Death,
- A life-threatening adverse event (see section [8.1.3](#))
- Inpatient hospitalization or prolongation of existing hospitalization
 - A hospitalization/admission that is pre-planned (i.e., elective or scheduled surgery arranged prior to the start of the study), a planned hospitalization for pre-existing condition, or a procedure required by the protocol, without a serious deterioration in health, is not considered a serious adverse event.
 - A hospitalization/admission that is solely driven by non-medical reasons (e.g., hospitalization for patient or subject convenience) is not considered a serious adverse event.
 - Emergency room visits or stays in observation units that do not result in admission to the hospital would not be considered a serious adverse event. The reason for seeking medical care should be evaluated for meeting one of the other serious criteria.

- Persistent or significant incapacity or substantial disruption of the ability to conduct normal life functions
- A congenital anomaly/birth defect
- Important medical events that may not result in death, be life-threatening, or require hospitalization may be considered a serious adverse drug experience when, based upon appropriate medical judgment, they may jeopardize the patient or subject and may require medical or surgical intervention to prevent one of the outcomes listed in this definition.

8.1.3 Life-threatening

An adverse event or suspected adverse reaction is considered "life-threatening" if, in the view of either the investigator or sponsor, its occurrence places the patient or subject at immediate risk of death. It does not include an adverse event or suspected adverse reaction that, had it occurred in a more severe form, might have caused death. (21CFR312.32).

8.1.4 Severity

The severity of each Adverse Event will be assessed utilizing the CTCAE version 5.

8.1.5 Relationship to Study Product

All AEs will have their relationship to study product assessed using the terms: related or not related.

- Related – There is a reasonable possibility that the study product caused the adverse event. Reasonable possibility means that there is evidence to suggest a causal relationship between the study product and the adverse event.
- Not Related – There is not a reasonable possibility that the administration of the study product caused the event.

8.2 ASSESSMENT OF SAFETY EVENTS

AE information collected will include event description, date of onset, assessment of severity and relationship to study product and alternate etiology (if not related to study product), date of resolution of the event, seriousness and outcome. The assessment of severity and relationship to the study product will be done only by those with the training and authority to make a diagnosis and listed on the Form FDA 1572 as the site principal investigator or sub-investigator. AEs occurring during the collection and reporting period will be documented appropriately regardless of relationship. AEs will be followed through resolution.

SAEs will be:

- Assessed for severity and relationship to study product and alternate etiology (if not related to study product) by a licensed study physician listed on the Form FDA 1572 as the site principal investigator or sub-investigator.
- Recorded on the appropriate SAE report form, the medical record and captured in the clinical database.
- Followed through resolution by a licensed study physician listed on the Form FDA 1572 as the site principal investigator or sub-investigator.

For timeframe of recording adverse events, please refer to section **6.1**. All serious adverse events recorded from the time of first investigational product administration must be reported to the sponsor.

8.3 REPORTING OF SERIOUS ADVERSE EVENTS

Any AE that meets protocol-defined serious criteria or meets the definition of Adverse Event of Special Interest that require expedited reporting must be submitted immediately (within 24 hours of awareness) to OSRO Safety using the CCR SAE report form.

All SAE reporting must include the elements described in section **8.2**.

SAE reports will be submitted to the Center for Cancer Research (CCR) at: [contact] and to the CCR PI and study coordinator. CCR SAE report form and instructions can be found at:

<https://ccrod.cancer.gov/confluence/display/CCRCRO/Forms+and+Instructions>

Following the assessment of the SAE by OSRO, other supporting documentation of the event may be requested by the OSRO Safety and should be provided as soon as possible.

8.4 SAFETY REPORTING CRITERIA TO THE PHARMACEUTICAL COLLABORATORS

All SAEs, regardless of attribution, will be reported to the manufacturer within 24 hours of learning of the events. For initial SAE reports, Investigators should record all case details that can be gathered within 24 hours on a MedWatch Form 3500a and submit the report via email to:

[name]
Chief, Nuclear Medicine Department's Positron Emission Tomography Section
Email address: [contact]

And

[name] via email address: [contact]

Relevant follow-up information should be submitted to the manufacturer as soon as it becomes available and/or upon request.

8.5 REPORTING PREGNANCY

All required pregnancy reports/follow-up to OSRO will be submitted to: [contact] and to the CCR PI and study coordinator. Forms and instructions can be found here:

<https://ccrod.cancer.gov/confluence/display/CCRCRO/Forms+and+Instructions>

8.5.1 Paternal exposure

Male patients should refrain from fathering a child or donating sperm during the study and for 6 months after the last treatment with SBRT and 2 months after the last 18F-DCFPyL PET/CT.

Pregnancy of the patient's partner is not considered to be an AE. The outcome of all pregnancies occurring from the date of the first dose until 6 months after the last treatment with SBRT and 2 months after the last 18F-DCFPyL PET/CT should, if possible, be followed up and documented. Pregnant partners may be offered the opportunity to participate in an institutional pregnancy

registry protocol (e.g., the NIH IRP pregnancy registry study) to provide data about the outcome of the pregnancy for safety reporting purposes.

8.6 REGULATORY REPORTING FOR STUDIES CONDUCTED UNDER CCR-SPONSORED IND

Following notification from the investigator, CCR, the IND sponsor, will report any suspected adverse reaction that is both serious and unexpected. CCR will report an AE as a suspected adverse reaction only if there is evidence to suggest a causal relationship between the study product and the adverse event. CCR will notify FDA and all participating investigators (i.e., all investigators to whom the sponsor is providing drug under its INDs or under any investigator's IND) in an IND safety report of potential serious risks from clinical trials or any other source, as soon as possible, in accordance to 21 CFR Part 312.32.

All serious events will be reported to the FDA at least annually in a summary format.

8.7 SPONSOR PROTOCOL DEVIATION REPORTING

A Protocol Deviation is defined as any non-compliance with the clinical trial Protocol, Manual of Operational Procedures (MOP) and other Sponsor approved study related documents, GCP, or protocol-specific procedural requirements on the part of the participant, the Investigator, or the study site staff inclusive of site personnel performing procedures or providing services in support of the clinical trial.

It is the responsibility of the study Staff to document any protocol deviation identified by the Staff or the site Monitor in the CCR Protocol Deviation Tracking System (PDTs) online application. The entries into the PDTs online application should be timely, complete, and maintained per CCR PDTs user requirements.

In addition, any deviation to the protocol should be documented in the participant's source records and reported to the reviewing IRB per their guidelines. OSRO required protocol deviation reporting is consistent with E6(R2) GCP: Integrated Addendum to ICH E6(R1): 4.5 Compliance with Protocol; 5.18.3 (a), and 5.20 Noncompliance; and ICH E3 16.2.2 Protocol deviations.

9 CLINICAL MONITORING

Clinical site monitoring is conducted to ensure:

- that the rights of the participants are protected;
- that the study is implemented per the approved protocol, Good Clinical Practice and standard operating procedures; and,
- the quality and integrity of study data and data collection methods are maintained.

Monitoring for this study will be performed by NCI CCR Office of Sponsor and Regulatory Oversight (OSRO) Sponsor and Regulatory Oversight Support (SROS) Services contractor. Clinical site monitoring activities will be based on OSRO standards, FDA Guidance E6(R2) Good Clinical Practice: Integrated Addendum to ICH E6(R1) March 2018, and applicable regulatory requirements.

Details of clinical site monitoring will be documented in a Clinical Monitoring Plan (CMP) developed by OSRO. CMPs will be protocol-specific, risk-based and tailored to address human subject protections and integrity of the study data. OSRO will determine the intensity and

frequency of monitoring based on several factors, including study type, phase, risk, complexity, expected enrollment rate, and any unique attributes of the study and the site. The Sponsor will conduct a periodic review of the CMP to confirm the plan's continued appropriateness. A change to the protocol, significant or pervasive non-compliance with GCP, or the protocol may trigger CMP updates.

OSRO SROS Monitoring visits and related activities will be conducted throughout the life cycle of each protocol. The first activity is before the study starts to conduct a Site Assessment Visit (SAV) (as warranted), followed by a Site Initiation Visit (SIV), Interim Monitoring Visit(s) (IMVs), and a study Close-Out Visit (COV).

Some monitoring activities may be performed remotely, while others will occur at the study site(s). Monitoring visit reports will describe visit activities, observations, and associated action items or follow-up required for resolution of any issues, discrepancies, or deviations. Monitoring reports will be distributed to the study PI, NCI CCR QA, CCR Protocol Support Office, coordinating center (if applicable), and the Sponsor regulatory file.

The site Monitor will inform the study team of any deviations observed during monitoring visits. If unresolved, the Monitor will request that the site Staff enter the deviations in the CCR Protocol Deviation Tracking System (PDTs) for deviation reporting to the Sponsor and as applicable per institutional and IRB guidance.

10 STATISTICAL CONSIDERATIONS

This is a single-institution, two-arm, Phase I trial, where patients with locally recurrent prostate cancer after prior radiotherapy will receive image-guided, focally dose escalated SBRT to the sites of local recurrence. Patients will be treated with escalated doses of radiation with the escalation on each arm occurring in parallel, and inclusion on each arm based on prior radiation treatment received. The primary endpoints will be to define the MTD of this approach. The secondary endpoints include to define DLTs, to describe the rate of 1 and 2-year biochemical relapse free survival (Phoenix criteria), to evaluate DCFPyL imaging as a method to detect locally recurrent prostate cancer after irradiation, and to define the quality of life changes that occur during and after this treatment. Exploratory endpoints include description of decision regret in patients who failed treatment and are successfully or unsuccessfully salvaged, evaluation of a personalized mutation panel for detection of early recurrence, and evaluation for the presence of neuroendocrine markers and markers of resistance in radio-recurrent prostate cancer.

10.1 STATISTICAL HYPOTHESIS

- Primary Endpoint: Define the maximum tolerated dose (MTD) of image-guided, focally dose escalated prostate SBRT in patients with a local recurrence of prostate cancer after prior radiotherapy. Assessment of toxicities for dose escalation will occur through 3 weeks after SBRT.
- Secondary Endpoints:
 - Define the dose-limiting toxicities and toxicity profile of image-guided, focally dose escalated prostate SBRT in patients previously treated with radiotherapy. Assessment of toxicities for dose escalation will occur through 3 weeks after SBRT.

- Describe the rate of PSA control (biochemical progression free survival, bPFS) at 1 and 2 years after treatment with focally dose escalated SBRT for locally recurrent prostate cancer after irradiation. We hypothesize that the rate of PSA control (bPFS) will compare favorably to the 75% rate obtained with brachytherapy in several previously published series.
- Describe the effects of focally dose escalated prostate SBRT on patient reported outcomes (SHIM, AUA Symptom Index, EPIC-26) in patients previously treated with radiotherapy. We hypothesize a reduction in quality of life (urinary and gastrointestinal side effects) after re-irradiation that persists for several months but returns to baseline in most patients by 2 years after treatment. We hypothesize that erectile dysfunction will progress after reirradiation without improvement over time.
- Evaluate 18F-DCFPyL imaging as a method to detect locally recurrent prostate cancer after radiation. We hypothesize that 18F-DCFPyL will have a high positive predictive value and sensitivity for diagnosing recurrent prostate cancer.

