1.2.1 Salvage reirradiation

Most studies of re-irradiation for locally recurrent prostate cancer after prior irradiation have used prostate brachytherapy to deliver a high radiation dose to the prostate gland (14-21). Brachytherapy is highly conformal and allows for lower exposures to normal tissues than conventionally fractionated radiotherapy. In the context of brachytherapy, a sufficient number of catheters must be inserted to obtain an optimal dose distribution, making focal dosing challenging. Some small series have used fusion of MRI to guide focal brachytherapy (25, 26). These methods were feasible, however there was a substantial rate of genitourinary toxicity with this approach, likely due to the use of normal tissue constraints similar to the definitive setting. Of note, with brachytherapy approaches, the dose to structures such as the urethra may be quite large compared to those delivered with EBRT approaches. Several published series of salvage brachytherapy have reported encouraging rates of biochemical control at 5 years of 65-85%, with cause specific survivals of 80-95% (14-21). Thus, these results compare favorably with the salvage prostatectomy approaches in a cohort of patients with a higher incidence of substantial co-morbidities.

Because brachytherapy approaches are technically demanding and can have an increased rate of toxicity after prior irradiation, few practitioners offer them in the setting of recurrence. Brachytherapy also requires some form of anesthesia, and in some cases an overnight hospitalization and temporary indwelling urine catheter until acute urinary symptoms resolve. The development of SBRT approaches that can be provided as an outpatient procedure without anesthesia, would enhance patient and practitioner acceptance.

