3.5 MONITORING DURING STUDY

Six months following treatment, patients in both arms will undergo repeat 18F-DCFPyL imaging only if pretreatment imaging was informative. Serial PSA and serial correlative studies will be collected for two years post-treatment.

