6.3.3 Progression-Free Survival

Biochemical progression free survival (bPFS) will be evaluated on this trial as a secondary endpoint. bPFS is defined as the duration of time from start of treatment to time of PSA progression or death, whichever occurs first. PSA progression (also known as biochemical failure) is defined based on elevation of PSA 2 ng/dL beyond the post-treatment nadir PSA, using the Phoenix criteria (47). A total of 2 PSA values separated by at least 1 month are required to document biochemical recurrence and to reduce the risk of mistakenly classifying a PSA “bounce” as a failure. If the PSA remains elevated, the date of failure will be backdated to the first PSA measurement that exceeded 2 ng/dL above the nadir. Only PSA values collected at the NIH Clinical Center will be used to evaluate disease status given the variability in ranges obtained in different laboratories. Patients who have been treated with androgen deprivation therapy within 3 months before or during this study will not be evaluable for the bPFS endpoint

until their testosterone is within the institutional limit of normal for at least two sequential measurements spaced by 1 month.

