10.2 SAMPLE SIZE DETERMINATION

Initially, the planned sample size is a minimum of 4 evaluable patients (2 per arm) and a maximum of 48 evaluable patients (24 evaluable patients maximum per arm). As of amendment version dates 04/13/2021 and 10/12/2021, determination has been made not to escalate either arm to dose level 3. Accordingly, a maximum of 42 evaluable patients may be enrolled (21 evaluable patients maximum per arm). Estimates for sample size are based on the assumption that all dose levels will accrue a maximum of patients, thus sample size is likely over-estimated. We do not anticipate drop out during treatment or follow-up, however that remains a possibility. We anticipate drop out would be minimal as we tend to accrue these patients from mainly the local area. To allow for a small number of patients who drop out or are not evaluable, we will set the accrual ceiling at 46.

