10.4.3 Analysis of the Secondary Endpoints

- Define the dose-limiting toxicities and toxicity profile of image-guided, focally dose escalated prostate SBRT in patients previously treated with radiotherapy: DLTs will be reported descriptively.
- Describe the rate of PSA control (bPFS, PSA < 2 ng/dL above post SBRT nadir) at 1 and 2 years after treatment with focally dose escalated SBRT for locally recurrent prostate cancer after irradiation: bPFS will be estimated by the Kaplan-Meier survival analysis and effects of clinical variables on bPFS will be assessed by the Cox proportional hazards model.
- Describe the effects of focally dose escalated prostate SBRT on patient reported outcomes (SHIM, AUA Symptom Index, EPIC-26) in patients previously treated with radiotherapy. The quality of life scores will be summarized at baseline and for each visit. Linear mixed effects model will be used to model quality of life scores at baseline and during and after treatment in which random intercept and random slope are used to account for patient-specific trajectory of quality of life scores. Changes of quality of life scores during and after treatment will be calculated from the estimated linear mixed effect model.
- Evaluate 18F-DCFPyL imaging as a method to detect locally recurrent prostate cancer after radiation. The sensitivity and specificity of DCFPyL for detecting locally recurrent prostate cancer (at baseline) will be reported using biopsy as the gold standard.

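### Section 10.1 compares 1- and 2-year bPFS with a 75% brachytherapy rate that has no stated time point or event definition and is probably a 5-year figure

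*Combined protocol and SAP*

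**What the plan says.** Under the secondary endpoints, section 10.1 sets the aim: "Describe the rate of PSA control (biochemical progression free survival, bPFS) at 1 and 2 years after treatment". It then adds the hypothesis that this rate "will compare favorably to the 75% rate obtained with brachytherapy in several previously published series". Section 10.1 does not cite the series, say at what time the 75% was observed, or say what counted as a failure.

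Other sections bear on how the 75% should be read:

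- Section 1.2.1 says that several salvage brachytherapy series reported "encouraging rates of biochemical control at 5 years of 65-85"%, citing references 14 to 21. Cause-specific survival is given separately. No other brachytherapy control rate appears in the document.
- Section 3.5 limits follow-up: "Serial PSA and serial correlative studies will be collected for two years post-treatment". The calendar in section 3.6 likewise ends at 24 months.
- Section 6.3.3 defines bPFS from start of treatment "to time of PSA progression or death, whichever occurs first", with PSA progression by the Phoenix rule.
- Section 10.4.3 plans that "bPFS will be estimated by the Kaplan-Meier survival analysis", with a Cox model for clinical variables. It plans no test against 75%.
- Section 10.2 caps enrolment at 42 evaluable patients, 21 per arm.

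**The concern.** A survival proportion means little without its time point. If the 75% is a 5-year rate, the plan sets an early SBRT result against a late brachytherapy result. A bPFS curve can only stay level or fall, so the brachytherapy rate at 1 or 2 years would be at least 75%, and higher if any failures came after that. A 2-year SBRT result a little above 75% could then be reported as favourable although it lay below the brachytherapy result at the same time.

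The 75% is the only numerical yardstick that section 10.1 gives for PSA control, so it is likely to frame how that endpoint is described.

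**Working it through.** **Inputs.** From the document: 75% (section 10.1); 65-85% at 5 years (1.2.1); SBRT assessment at 1 and 2 years (10.1); two years of PSA (3.5); at most 42 evaluable patients, 21 per arm (10.2). Assumed: 75% is a 5-year rate, events are defined alike on both sides unless stated otherwise, and follow-up to 2 years is complete.

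**1. Where 75% could come from.** The plan shows no derivation. The one match in the document is the midpoint of the 5-year range: (65 + 85)/2 = 75.

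**2. Direction, with no hazard model.** Let S5 be the 5-year rate and f the share of 5-year failures that occur after year 2. Then S2 = S5 + (1 − S5)·f = 0.75 + 0.25f, which is never below 0.75. An observed 80% at 2 years falls below the matched value once f exceeds (0.80 − 0.75)/0.25 = 20%.

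**3. Size, with a hazard model.** S(t) = S5^((t/5)^k), where k = 1 is constant hazard. The shape range 0.5 to 2 is an assumption.

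| 5-year rate | 2-year equivalent, k = 0.5 | k = 1 | k = 2 |
|---|---|---|---|
| 65% | 76.2% | 84.2% | 93.3% |
| 75% | 83.4% | 89.1% | 95.5% |
| 85% | 90.2% | 93.7% | 97.4% |

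For 75%, constant hazard: 0.75^0.4 = 0.891 at 2 years and 0.75^0.2 = 0.944 at 1 year. The 1-year range over the same shapes is 87.9% to 98.9%.

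**4. What an observed rate above 75% would show (constant hazard, exact binomial).** More than 75% means at least 16/21 or at least 32/42.

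- Treatment equal to brachytherapy (true 2-year rate 89.1%): probability 97.9% with 21 patients, 99.6% with 42.
- Treatment with twice the brachytherapy hazard (true 2-year rate 0.75^0.8 = 79.4%; 5-year rate 0.75² = 56.3%): probability 74.8% with 21, 76.8% with 42.

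**5. If the trial counts deaths and the series did not.** Assume 2% other-cause mortality per year, so multiply the 2-year equivalent by 0.98² = 0.9604.

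- k = 1: 0.891 × 0.9604 = 85.6%.
- k = 0.5: 0.834 × 0.9604 = 80.1%.

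The mortality m that would close the 2-year gap solves S2·(1 − m)² = 0.75. It is 5.1%, 8.3% and 11.4% per year for k = 0.5, 1 and 2. A different PSA-failure rule in the series would also move the benchmark, by an amount and in a direction that the document does not allow one to calculate.

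**6. Precision.** 34/42 (81%) has an exact 95% CI of 65.9-91.4%; 17/21 (81%) has 58.1-94.6%. Both contain 75% and 89.1%.

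**The case against.** The strongest reply is that the harm depends on sources the reader does not have. The 5-year reading rests on a midpoint and similar phrasing in section 1.2.1, and the 75% could be an earlier rate from some of the same series. That stands. A reader might infer that the plan demonstrably compares a 2-year rate with a 5-year one. The document shows only that the time point is missing and that the one dated brachytherapy rate is at 5 years.

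A second reply is that differing event definitions might remove the advantage. This also stands in part. It is tempting to say that counting deaths could not plausibly close the gap, but that depends on the hazard shape. At shape 0.5 with 2% annual mortality, the matched value is 80.1%, level with an observed 80%. At the 65% end of the range, shape 0.5 gives 76.2% even before any offset. The PSA-failure rule in the series is unknown as well.

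A third reply concerns section 10.4.3, which glosses the endpoint as "bPFS, PSA < 2 ng/dL above post SBRT nadir) at 1 and 2 years after treatment" and does not mention death. A reader might infer a rival definition. The same term is formally defined in 6.3.3, so the gloss can fairly be read as shorthand for the PSA threshold.

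Finally, the endpoint is descriptive, and the intervals are too wide to separate 75% from 89%. Section 1.2.1 also offers a dated figure for context: 82% at 2 years by the Phoenix rule in a 29-patient SBRT series. This limits the consequence. It does not make an undated benchmark interpretable, and wide intervals are a further reason not to call a point estimate favourable.

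**Conclusion.** The point holds at low severity. Section 10.1 leaves the time point and event definition of its benchmark unstated, and the most likely reading in the document is a 5-year rate set against 1- and 2-year results. On that reading, with matching events, the comparison favours SBRT whatever the hazard shape. The gap at 2 years is about 14 points under constant hazard (89.1% against 75%) and about 8 to 21 points over Weibull shapes 0.5 to 2. If the series did not count deaths, the gap is smaller. If their PSA-failure rule differed, its size is unknown.

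A reader might infer that the trial's design or conclusions are biased. The document does not support that: no test, margin, sample size or dose decision uses the 75%. Only the wording of a descriptive secondary result is at risk.

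**What to change.** In section 10.1, state the source, time point and event definition of the 75%. Then report 1- and 2-year Kaplan-Meier bPFS with 95% confidence intervals, and compare them only with published salvage brachytherapy rates at the same time point and with the same event definition. If the 75% proves to be a 1- or 2-year rate with matching events, keep it for that time point only. If no matched rate is available, label the 5-year figure as context and make no claim that SBRT compares favourably. The model-based conversions above show size only and should not become the benchmark.

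The cost is a sentence or two in section 10.1 and a check of the cited series; no new trial data are needed. The downside is that the benchmark may become less favourable to SBRT, or that the comparison may be lost.
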